13.6 Determination of Sample Size

This is an observational study and no hypothesis is being tested. Collection of long term safety and MG-ADL scores are required to demonstrate that amifampridine is safe and well tolerated in the MG population and if there is a change in dose requirements with time.

13.7 Changes in the Conduct of the Study or Planned Analyses

Any change in study conduct considered necessary by the Investigator will be made only after consultation with Catalyst, who will then issue a formal protocol amendment to implement the change. The only exception is when an Investigator considers that a patient's safety is compromised without immediate action. In these circumstances, immediate approval of the chairman of the IRB/IEC/REB must be sought, and the Investigator should inform Catalyst and the full IRB/IEC/REB within 2 working days after the emergency occurs.

Except for minor administrative or typographical changes, the IRB/IEC/REB must review and approve all protocol amendments. Protocol amendments that influence patient risk or the study objectives, or require revision of the ICF, must receive approval from the IRB/IEC/REB prior to their implementation.

When a protocol amendment substantially alters the study design or the potential risks or burden to patients, the ICF will be amended and approved by Catalyst and the IRB/IEC/REB, and all active patients must again provide informed consent.

Note: If discrepancies exist between the text of the statistical analysis as planned in the protocol, and the final SAP, a protocol amendment will not be issued, and the SAP will prevail.

	MSK-003	Page 40
---	---------	---------

14 COMPENSATION, INSURANCE, AND INDEMNITY

There will be no charge to study patients to be in this study. Catalyst will pay all costs of tests, procedures, and treatments that are part of this study (as included in the site budget). In addition, after IRB/IEC/REB approval, Catalyst may reimburse the cost of travel for study-related visits. Catalyst will not pay for any hospitalizations, tests, or treatments for medical problems of any sort, whether or not related to the study patient's disease that are not part of this study. Costs associated with hospitalizations, tests, and treatments should be billed and collected in the way that such costs are usually billed and collected.

The Investigator should contact Catalyst immediately upon notification that a study patient has been injured by the IP or by procedures performed as part of the study. Any patient who experiences a study-related injury should be instructed by the Investigator to seek medical treatment at a pre-specified medical institution if possible, or at the closest medical treatment facility if necessary. The patient should be given the name of a person to contact to seek further information about, and assistance with, treatment for study-related injuries. The treating physician should bill the patient's health insurance company or other third-party payer for the cost of this medical treatment. If the patient has followed the Investigator's instructions, Catalyst will pay for reasonable and necessary medical services to treat the injuries caused by the IP or study procedures, if these costs are not covered by health insurance or another third party that usually pays these costs. In some jurisdictions, Catalyst is obligated by law to pay for study-related injuries without prior recourse to third party payer billing. If this is the case, Catalyst will comply with the law.

15 CASE REPORT FORMS AND SOURCE DOCUMENTS

The CRO data management department or designee will perform all data management activities, including the writing of a data management plan outlining the systems and procedures to be used.

Electronic case report forms (eCRFs) will be provided. The eCRF system, and procedures, and electronic signatures follow ICH requirements and applicable laws and local regulations.

All system users will be trained on the eCRF before being granted system access. In the event of an entry error, or if new information becomes available, users will correct the value by deselecting the erroneous response and then selecting or entering the factual response. The

	MSK-003	Page 41
---	---------	---------

documented audit trail will include the reason for the change, the original value, the new value, the time of the correction and the identity of the operator.

In the application, study data on the eCRFs will be verified to the source data, which necessitates access to all original recordings, laboratory reports, and patient records. In addition, all source data should be attributable (signed and dated). The Investigator must therefore agree to allow direct access to all source data. Patients must also allow access to their medical records, and patients will be informed of this and will confirm their agreement when giving informed consent. The Investigator must review and electronically sign the completed eCRF casebook to verify its accuracy. A CRA designated by Catalyst will compare the eCRFs in the application with the original source documents at the study site and evaluate them for completeness and accuracy before designating them as “Source Data Verified” in the application. If an error is discovered at any time or a clarification is needed, the Data Manager, CRA, or designee, will create an electronic query on the associated field. Site personnel will then answer the query by either correcting the data or responding to the query. The Data Manager or CRA will then review the response and determine either to close the query or re-query the site if the response does not fully address the question. This process will be repeated until all open queries are answered and closed.

The CRO’s data management department may receive electronic transfers of laboratory data from the site’s local laboratory as well as other data from third-party vendors as appropriate.

The Investigator will then electronically sign the casebook, specifying that the information on the eCRFs is accurate and complete. An electronic copy of each site’s casebooks will be sent to each site for retention with other study documents.

16 STUDY MONITORING AND AUDITING

Qualified individuals approved and/or designated by Catalyst will monitor all aspects of the study according to GCP and SOPs for compliance with applicable government regulations. The monitoring will take place on site as well as remotely as the monitors can view all clinical data electronically and can follow-up with any queries for more information. The Investigator agrees to allow these monitors direct access to the clinical supplies, dispensing, and storage areas and to the clinical files, including original medical records, of the study patients, and, if requested, agrees to assist the monitors. The Investigator and staff are

	MSK-003	Page 42
---	---------	---------

responsible for being present or available for consultation during routinely scheduled site visits conducted by Catalyst or its designees.

Members of Catalyst's GCP Quality Department or designees may conduct an audit of a clinical site at any time before, during, or after completion of the study. The Investigator will be informed if an audit is to take place and advised as to the scope of the audit.

Representatives of the FDA or other regulatory agencies may also conduct an audit of the study. If informed of such an inspection, the Investigator should notify Catalyst immediately. The Investigator will ensure that the auditors have access to the clinical supplies, study site facilities, original source documentation, and all study files.

17 RETENTION OF RECORDS

The Investigator must retain all study records required by Catalyst and by the applicable regulations in a secure and safe facility. The Investigator must consult a Catalyst representative before disposal of any study records and must notify Catalyst of any change in the location, disposition or custody of the study files. The Investigator/institution must take measures to prevent accidental or premature destruction of essential documents, that is, documents that individually and collectively permit evaluation of the conduct of a study and the quality of the data produced, including paper copies of study records (e.g. patient charts) as well as any original source documents that are electronic as required by applicable regulatory requirements.

All study records must be retained for at least 2 years after the last approval of a marketing application in an ICH region and until (1) there are no pending or contemplated marketing applications in an ICH region or (2) at least 2 years have elapsed since the formal discontinuation of clinical development of the IP. The Investigator/institution should retain patient identifiers and records for at least 15 years after the completion or discontinuation of the study. Patient files and other source data must be kept for the maximum period of time permitted by the hospital, institution or private practice. These documents should be retained for a longer period, however, if required by the applicable regulatory requirements or by a Catalyst agreement. Catalyst must be notified and will assist with retention should Investigator/institution be unable to continue maintenance of patient files. It is the responsibility of Catalyst to inform the Investigator /institution as to when these documents no longer need to be retained.

	MSK-003	Page 43
---	---------	---------

18 USE OF INFORMATION AND PUBLICATION

Catalyst recognizes the importance of communicating medical study data and therefore encourages their publication in reputable scientific journals and at seminars or conferences. The details of the processes of producing and reviewing reports, manuscripts, and presentations based on the data from this study will be described in the Clinical Trial Agreement between Catalyst and the institution of the Investigator.

20 INVESTIGATOR RESPONSIBILITIES

20.1 Conduct of Study and Protection of Human Patients

The Investigator will ensure that:

- He or she will conduct the study in accordance with the relevant, current protocol and will only make changes in a protocol after notifying the sponsor, except when necessary to protect the safety, rights, or welfare of patients.
- He or she will personally conduct or supervise the study.
- He or she will inform any potential patients, or any persons used as controls, that the drugs are being used for investigational purposes and he or she will ensure that the requirements relating to obtaining informed consent in compliance with ICH E6 (Section 4.8), and other applicable local regulations, are met.
- He or she will report to the sponsor adverse experiences that occur during the investigation in compliance with the standard operating procedures and policies of the IRB/IEC/REB and with applicable regulatory requirements.
- He or she has read and understands the information in the Investigator's Brochure, including potential risks and side effects of the drug.
- His or her staff and all persons who assist in the conduct of the study are informed about their obligations in meeting the above commitments.
- He or she will ensure that adequate and accurate records are kept in accordance with ICH and GCP requirements and to ensure those records are available for inspection.
- He or she will ensure that the IRB/IEC/REB complies with ICH and GCP requirements, and other applicable regulations, and conducts initial and ongoing reviews and approvals of the study. He or she will also ensure that any change in research activity and all problems involving risks to human patients or others are reported to the IRB/IEC/REB. Additionally, he or she will not make any changes in the research without IRB/IEC/REB approval, except where necessary to eliminate apparent immediate hazards to human patients.
- He or she agrees to comply with all other requirements regarding the obligations of clinical Investigators and all other pertinent ICH and GCP requirements.
- He or she agrees to comply with electronic signature requirements in accordance with ICH requirements and applicable laws and local regulations.

APPENDIX 1: MYASTHENIA GRAVIS-SPECIFIC ACTIVITIES OF DAILY LIVING (MG-ADL)

The MG-ADL is a self-report scale designed to assess the patient's MG symptoms and functional performance of activities of daily living. Eight items as listed below will be assessed by the patient at the protocol specified time points (see [Table 1](#)).

					Score
Grade	0	1	2	3	(0, 1, 2, 3)
1. Talking	Normal	Intermittent slurring of nasal speech	Constant slurring or nasal, but can be understood	Difficult to understand speech	
2. Chewing	Normal	Fatigue with solid food	Fatigue with soft food	Gastric tube	
3. Swallowing	Normal	Rare episode of choking	Frequent choking necessitating changes in diet	Gastric tube	
4. Breathing	Normal	Shortness of breath with exertion	Shortness of breath at rest	Ventilator dependence	
5. Impairment of ability to brush teeth or comb hair	None	Extra effort, but no rest periods needed	Rest periods needed	Cannot do one of these functions	
6. Impairment of ability to arise from a chair	None	Mild, sometimes uses arms	Moderate, always uses arms	Severe, requires assistance	
7. Double vision	None	Occurs, but not daily	Daily, but not constant	Constant	
8. Bothersome eyelid droop	None	Occurs, but not daily	Daily, but not constant	Constant	
					MG-ADL score
					(items 1-8)

| AChR-MG | Acetylcholine receptor Myasthenia Gravis |
| CRF | Case Report Form |
| DBP | Diastolic Blood Pressure |
| DSUR | Development Safety Update Report |
| ECG | Electrocardiograms |
| FDA | Food and Drug Administration |
| ICF | Informed Consent Form |
| ICH | International Committee for Harmonization |
| MedDRA | Medical Dictionary for Drug Regulatory Affairs |
| MG-ADL | Myasthenia Gravis Activities of Daily Living |
| MuSK-MG | Muscle-specific receptor tyrosine Kinase-Myasthenia Gravis |
| PBRS | Peachtree BioResearch Solution |
| PT | Preferred Term |
| SAE | Serious Adverse Events |
| SAP | Statistical Analysis Plan |
| SAS | Statistical Analysis System |
| SBP | Systolic Blood Pressure |
| SOC | System Organ Class |
| TEAE | Treatment-Emergent Adverse Events |
| US | United States |
| WHODRUG | World Health Organization Drug Dictionary |

1. INTRODUCTION

1.1 Objectives

The present long-term extension study will evaluate safety and tolerability of amifampridine on clinical laboratory test variables, ECGs, AEs, vital signs, physical examinations and the effects on MG-ADL score over several months in patients with MuSK-MG or AChR-MG. is needed to demonstrate that the product is safe and in patients with MG.

- The primary objective of the study is to evaluate the long-term safety and tolerability of amifampridine in patients with MuSK-MG; and with AChR-MG.
- The secondary objective of the study is to assess the effect of amifampridine phosphate on Myasthenia Gravis Activities of Daily Living Score (MG-ADL).

This Statistical Analysis Plan (SAP) corresponds to the Statistical Approach section of Clinical Protocol MSK-003, amendment, dated February 07, 2020, with additional changes included to the Version 1.0 dated 25 Oct 2022.

1.2 Design

The study will enroll those patients who have completed the MSK-002 study and after all final evaluations for that study have been completed, or those who demonstrated benefit after completing the dose titration period but failed to meet the randomization criteria on Day 0 of MSK-002.

The duration of participation for each patient is expected to be at least 9 months as patients may continue in the study until amifampridine is approved by Regulatory Agencies or the clinical development of amifampridine is terminated for this indication. In addition to amifampridine, patients will continue to receive previous concomitant medications, as needed.

After a new informed consent is signed and inclusion / exclusion criteria for the current protocol are satisfied, eligible patients will be given the optimal dose and dosing schedule that was identified in the Run-in Period from Protocol MSK-002.

The findings from the physical exam (including vital signs, weight); 12-lead ECG; clinical laboratory test results (including pregnancy testing) and any ongoing adverse events will be used as the baseline for the long-term safety evaluation.

The only efficacy measurement is the MG-ADL which will be completed every 3 or 6 months. Safety and tolerability assessments will be made every 3 or 6 months or more frequently at the discretion of the Investigator. The study will continue until amifampridine is approved by Regulatory Agencies or until development of the product for this indication is halted or until month 39 is reached. The Investigator may alter the dose and dosing frequency during the Long-Term Study as well as schedule additional clinic visits for any reason.

Patients will be seen in the clinic at the end of Months 3, 6, 9, 12, 15, 21, 27, 33 and 39. In between the 3-or 6-month visits, patients may also have telephone/video contact with the site, or unscheduled visits, if needed.

Any unused medication must be brought back to the clinic at each visit for drug accountability, and an additional supply will be dispensed.

2. ELABORATION OF STUDY PROTOCOL

2.1 Study Populations

- Safety Population: All enrolled patients who receive at least one dose of study drug will be included in the safety population.

All analyses will be performed on the safety population.

2.2 Study Endpoints

2.2.1 *Safety Endpoint*

Safety endpoints of this study are:

- Incidence of patients experiencing treatment-emergent adverse events (TEAEs)
- Incidence of patients experiencing study drug-related TEAEs
- Incidence of patients experiencing equal or greater than Grade 3 TEAEs
- Incidence of patients discontinuing from the study due to TEAEs
- Physical exam and weight
- Vital signs including systolic blood pressure (SBP) and diastolic blood pressure (DBP), heart rate, respiration, and body temperature
- Clinical laboratory tests, including hematology, chemistry and urinalysis
- Concomitant medication review
- Electrocardiogram (ECG) parameters

2.2.2 *Efficacy Endpoint*

Efficacy endpoint of this study is change in MG-ADL score over time.

2.3 Sample Size

The study is not powered with respect to any endpoint, but is an observational study to assess long term safety and lack of tolerance to the effects of amifampridine on MG-ADL. No sample size power calculation was conducted for this study.

3. STATISTICAL METHODS

3.1 General

All data will be analyzed using the Statistical Analysis System (SAS®; Version 9.2 or higher).

Continuous variables will be presented by descriptive statistics: n, mean, standard deviation, median, minimum, and maximum. Categorical variables will be tabulated by frequency count and percentage. No hypothesis testing will be performed.

3.1.1 *Display of Decimal Places*

Means and medians will be reported to one decimal place more than the original unit reported on the case report form (CRF) or by the laboratory/vendor. Standard deviations will be reported to two decimal places more than the original unit. Minimum and maximum values will be reported to the same number of decimal places displayed on the CRF or by the laboratory/vendor.

3.1.2 *Visit Windowing*

For Vital signs, ECG, Lab and physical exam, the following protocol-specified visits are further defined for summary tables as below.

- Screening Visit (Baseline): the day subject was screened following the ICF signing
- Follow-up visit (3 Months): the visit date was most close to 91 days after baseline visit.
- Follow-up visit (6 Months): the visit date was most close to 183 days after baseline visit.
- Follow-up visit (9 Months): the visit date was most close to 274 days after baseline visit.
- Follow-up visit (12 Months): the visit date was most close to 365 days after baseline visit.
- Follow-up visit (15 Months): the visit date was most close to 456 days after baseline visit.
- Follow-up visit (21 Months): the visit date was most close to 640 days after baseline visit.
- Follow-up visit (27 Months): the visit date was most close to 822 days after baseline visit
- Follow-up visit (33 Months): the visit date was most close to 1005 days after baseline visit
- Follow-up visit (39 Months): the visit date was most close to 1187 days after baseline visit

For completed subjects, Follow-up visit (39 Months) is considered End of study visit.

For discontinued subjects, if the assessments at the scheduled visit prior to the early termination (ET) visit were not done, the ET visit will be assigned as the prior scheduled visit. Otherwise, the ET visit will be assigned to the next scheduled visit.

Other visits will be listed as “Unscheduled Visits”, and data collected at unscheduled visits will not be included in the summary table, but will be presented in the data listings.

3.1.3 *Missing Data Handling*

In general, all categories that appear on the CRF and in summary table templates will be reported even if no patients reported that category (e.g., if there are no patients of a particular race). The “Missing” category displayed for categorical variables in summary table templates will only be displayed if missing observations are present. If no observations meet the criteria for inclusion in a data display (e.g., if there are no SAEs), the table or listing will be generated with a line in the body of the listing such as “None reported.”

No imputation will be conducted for the missing data.

3.1.4 *Sub-group Analyses*

All safety endpoints will be analyzed by MG type: MuSK-MG and AChR-MG.

3.2 *Subject Disposition, Demographics, Baseline Characters and Study Drug Compliance*

3.2.1 *Patient Disposition*

Study completion status will be summarized for all patients. The duration of treatment will be summarized for treated patients. Categories summarized will include patients who were planned, screened, screen failure, enrolled, received study drug, completed the study, were lost to follow-up, or withdrew early. Reasons for screen failure and withdrawal will be summarized.

3.2.2 *Protocol Deviations*

Individual protocol deviations will be presented in a data listing.

3.2.3 *Demographics and Baseline Characters*

Demographic characteristics of all patients enrolled will be summarized descriptively. The summary will include age, gender, race/ethnicity, height, weight.

3.2.4 *Study Drug Exposure*

The treatment duration (day), the total dose (mg) of study drug administered, average daily dose of study drug, and study drug compliance (%) will be tabulated.

- Treatment Duration (day) is calculated as The Last Dose Date – The First Dose Date +1. If the last dose date is missing, then the last visit date will be used.
- Total Dose (mg) will be calculated as the sum of the daily dose (mg) over the Treatment Duration, considering different doses during individual time periods within the study, as documented in the IP Accountability eCRF page.
- Average Daily Dose (mg) will be calculated as Total Dose (mg) / Treatment Duration (day). This will be calculated considering each time period and Daily dose during that period, as documented in the IP Accountability eCRF page.
- Study Drug Compliance (%): $100 \times \text{Total Dose Taken (mg)} / \text{Total Dose Prescribed (mg)}$

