Study Assessment or Event	Screening and Enrollment *	Study Month ± 1 week									
		3	6	9	12	15	21	27	33	39	End of Study ^g
Informed consent ^a	x										
Inclusion/Exclusion	x										
Complete physical exam ^b	x	x	x	x	x	x	x	x	x	x	x
Vital signs	x	x	x	x	x	x	x	x	x	x	x
12-Lead ECG	x	x	x	x	x	x	x	x	x	x	x
Clinical laboratory tests ^c	x	x	x	x	x	x	x	x	x	x	x
Pregnancy test ^d	x	x	x	x	x	x	x	x	x	x	x
Amifampridine Treatment	x	x	x	x	x	x	x	x	x	x	x
MG-ADL		x	x	x	x	x	x	x	x	x	x
Dispense IP ^e	x	x	x	x	x	x	x	x	x	x	x
IP Accountability		x	x	x	x	x	x	x	x	x	x
Adverse events/SAEs ^f	x	x	x	x	x	x	x	x	x	x	x
Concomitant medications	x	x	x	x	x	x	x	x	x	x	x

^a Informed consent must be obtained before any study procedures are performed.

^b Complete physical examination includes evaluation of all major body systems, including weight at all visits (Section 9.6.6).

^c Clinical laboratory tests include serum chemistry, hematology, and urinalysis.

^d Urine pregnancy tests will be obtained from female patients of childbearing potential.

^e Pharmacist will dispense sufficient amount of medication until the next clinic visit. All unused medication must be returned to the clinic for drug accountability.

^f SAE reporting commences after informed consent is signed. Non-serious adverse event reporting commences after the first dose of study drug for the current Long-Term Study.

^g End of Study or early termination visit if the last visit does not coincide the scheduled 3- or 6-month visit.

*These data may be obtained from Study MSK-002. If data not available, then the assessment should be repeated.

	MSK-003	Page 21
---	---------	---------

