9.3 Safety Blood Collection

Patients who experience a serious or severe AE should have, at the discretion of the Investigator, a blood sample drawn for safety labs as soon as possible after the AE has occurred.

Additional blood sampling may be performed at any time during the study if warranted to monitor patient safety.

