11.2.1 End of Study Visit

Patients will report to the study site at the end of the study and have the assessments and procedures listed below completed. This visit may be incorporated at the scheduled 3-or 6-month visit.

- Assessment of AEs/SAEs;
- Complete physical exam with weight;
- Vital signs (seated position), including SBP, DBP, heart rate, respiration, and body temperature;
- 12-Lead ECG;
- Clinical laboratory tests;
- Urine pregnancy test in females of childbearing potential only;
- Concomitant medications;
- IP accountability;
- MG-ADL

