3.3 Safety Analysis

3.3.1 *General*

All safety summaries will be presented overall for the safety population. The evaluation will take into account the recorded adverse events (AE), clinical laboratory tests, vital signs, physical exam, ECG assessments and concomitant medications.

3.3.2 *Adverse Events*

Since patients started taking study medication before enrolled the study, all AE reported are considered as treatment-emergent adverse events (TEAE).

Tabular summaries will be provided by indication for the number and percentage of patients with:

- Any TEAE by SOC and PT. This summary will include the number of unique events reported.
- Any study drug-related TEAE by SOC and PT
- Any TEAEs by SOC, PT and maximum severity
- Any treatment-emergent serious adverse event (TESAE) by SOC and PT
- Any TEAE that results in patient discontinuation from the study by SOC and Preferred Term (PT)

A listing of all adverse events will be provided. In addition, separate data listings will be presented for the following:

- Patient deaths

- Serious Adverse Events (SAEs)
- Listing of Grade 3 (Severe) or Grade 4 (Life-threatening) AEs
- Listing of AEs leading to study discontinuation

3.3.3 *Vital Signs*

A summary of values and changes from Baseline will be provided by vital signs parameter and visit of at 3, 6, 9, 12, 15, 21, 27, 33 and 39 months.

3.3.4 *Electrocardiogram (ECG)*

Each over-read ECG interval and change from baseline in each interval will be summarized descriptively by visit at 3, 6, 9, 12, 15, 21, 27, 33 and 39 months

Treatment-emergent cardiac abnormalities, as well as the overall interpretation, will be summarized. Treatment-emergent ECG findings considered by the investigator to be clinically significant will be presented only in a listing.

3.3.5 *Clinical Laboratory Assessments*

A summary of laboratory values and changes from Baseline will be provided by test and visit of at 3, 6, 9, 12, 15, 21, 27, 33 and 39 months. In addition, laboratory measures out of range or abnormal will be presented for each visit. Values deemed clinically significant by the Investigator will not be summarized, but will be presented in a listing.

3.3.6 *Physical Examinations*

The number and percent of patients with physical examination abnormalities will be summarized by body system and visit of at 3, 6, 9, 12, 15, 21, 27, 33 and 39 months.

3.3.7 *Concomitant Medications*

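### SAP 3.1.2 files early-termination safety values under a scheduled visit whatever their actual day, and keeps unscheduled values out of the summary tables with no worst-post-baseline summary: a cheap improvement to descriptive tables

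*SAP*

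**What the plan says.** SAP 3.1.2 defines the visits used in the summary tables for vital signs, ECG, laboratory tests and physical examination. Each scheduled visit is the one nearest a target day. For patients who discontinue, an ET visit fills the preceding scheduled visit if that was not done. For all other cases the text is: "Otherwise, the ET visit will be assigned to the next scheduled visit". No day limit is attached, and the protocol's window of plus or minus 1 week (Table 1 and section 11.2) is not carried over.

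The same section states: "For completed subjects, Follow-up visit (39 Months) is considered End of study visit". On anything else it says that "data collected at unscheduled visits will not be included in the summary table, but will be presented in the data listings".

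The protocol limits when a separate ET visit arises. Table 1, footnote g, describes it as "End of Study or early termination visit if the last visit does not coincide the scheduled 3- or 6-month visit", and section 11.2.1 adds: "This visit may be incorporated at the scheduled 3-or 6-month visit".

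In SAP 4.1, the laboratory, vital-sign and ECG tables (T11 to T17, T19 and T20) are by visit. SAP 3.3.4 also promises: "Treatment-emergent cardiac abnormalities, as well as the overall interpretation, will be summarized", without saying whether unscheduled ECGs count. SAP 3.5 includes unscheduled visits after the first dose among post-baseline visits, but no listed table is said to use them that way.

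**The concern.** Safety is the primary objective, and these four domains are safety endpoints in SAP 2.2.1. Two things follow from the rules as written.

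- A row labelled with a month can hold ET values measured months before or after that label. The Month 39 row can combine patients who left soon after Month 33 with patients who completed 39 months, and nothing in the table separates them.
- A peak between visits, such as a QTc or liver enzyme value from an extra check, appears in no by-visit table. It appears in a listing, or as an adverse event if the investigator considers it clinically significant. The protocol foresees such measurements. Section 9.3 says: "Patients who experience a serious or severe AE should have, at the discretion of the Investigator, a blood sample drawn for safety labs". Section 8.6.3 allows laboratory tests more often than scheduled.

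**Working it through.** **Inputs.** Target days 91, 183, 274, 365, 456, 640, 822, 1005 and 1187 after baseline (SAP 3.1.2). Visit window of 7 days either side (Protocol 11.2). Planned numbers of up to about 60 MuSK-MG and about 10 AChR-MG patients (Protocol synopsis). The documents give no number or timing of ET visits.

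**1. Reproduce the target days.** Months × 365.25/12 gives 91.31, 182.62, 273.94, 365.25, 456.56, 639.19, 821.81, 1004.44 and 1187.06. All nine stated targets agree within 1 day.

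**2. Gaps and mean displacement.** Assume ET days are spread evenly over the whole days strictly between two targets. The mean distance to the assigned target is then gap/2, whether the ET goes forward or back.

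| Interval | Gap (days) | Mean = gap/2 (days) |
|---|---|---|
| Baseline to Month 3 (forward only) | 91 | 45.5 |
| Month 3 to 6 | 92 | 46 |
| Months 6 to 9, 9 to 12, 12 to 15 | 91 each | 45.5 |
| Month 15 to 21 | 184 | 92 |
| Month 21 to 27 | 182 | 91 |
| Month 27 to 33 | 183 | 91.5 |
| Month 33 to 39 | 182 | 91 |

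Over the four later intervals: (183×92 + 181×91 + 182×91.5 + 181×91)/727 = 66,431/727 = 91.4 days, or 91.4/30.4375 = 3.0 months. Leaving out ET days within 7 days of either target does not change these later means, because the exclusion is symmetric. For comparison, assigning each ET to the nearest target would give a mean of 45.9 days after Month 15, with a maximum of 92.

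**3. How far a single value can move.** A completed visit may itself be a week early, and an ET just after it still goes forward. If Month 15 is done on Day 456 − 7 = 449 and the ET is on Day 450, the ET is filed at Day 640, a displacement of 640 − 450 = 190 days. Going backward, suppose Month 15 was missed and the ET is on Day 632, just outside the Month 21 window. It is filed at Day 456, 632 − 456 = 176 days away.

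**4. The Month 39 row.** If Month 33 is done on Day 1005 and the ET is on Day 1006, the value is tabulated at Day 1187, which is 181 days later, alongside the completers' End of Study values.

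**5. Weight of one misplaced value.** SAP 3.3.1 presents safety summaries overall; SAP 3.1.4 analyses them by MG type. At the planned numbers, one value is 1/70 = 1.4% of an overall row, 1/60 = 1.7% of a MuSK-MG row and 1/10 = 10% of an AChR-MG row. The share is larger where late rows hold fewer patients.

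**6. Tracing an unscheduled value.** SAP 3.1.2 keeps it out of the summary tables. Listings DL07 to DL09 and DL11 to DL13 show it. Protocol 8.6.2, 8.6.3, 8.6.5 and 8.6.6 have clinically significant findings recorded as adverse events, which reach the TEAE tables. No numeric summary of the worst post-baseline value is named anywhere in the SAP.

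**The case against.** The study is descriptive and tests no hypothesis. The ET rule is prespecified, leaves no discretion, and keeps leavers' last values in the tables. An ET row is another convention, and it has the fault of pooling leavers from different times. Keeping event-driven values out of by-visit means is sound. Laboratory samples under Protocol 9.3 follow an event that is already in the adverse event tables, and some repeat samples only follow up a value already tabulated. With about 70 patients, the listings can be read through. Worst values rise with follow-up length and visit frequency, and there is no comparator.

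Most of this stands, and it sets the weight of the point. It does not remove two facts: the month label on an ET value can be far from the day of measurement, and recording a change as an adverse event depends on the investigator's view, so it does not replace a numeric summary.

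A reader might go further in four ways that the documents do not support:

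- That ET values are typically 3 months out. This needs the even-spread assumption; the documents give no ET timing.
- That every ET is displaced. An ET that coincides with a scheduled visit can simply be that visit.
- That unscheduled values can never enter a by-visit row. Read literally, the nearest-to-target rule could select an extra visit.
- That safety signals are hidden or the tables biased in a known direction. The values are listed, clinically significant changes should become adverse events, and no direction can be derived.

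**Conclusion.** The point holds as a cheap improvement to descriptive safety tables. Off-schedule ET values are filed without regard to their actual day. Displacement is bounded only by the visit interval, so it can reach about 3 months up to Month 15 and about 6 months after it, with 190 days in the worked example. The 91-day mean after Month 15 is conditional on evenly spread ET days. The row weights of 1.4%, 1.7% and 10% rest on the planned numbers and on whether a table is overall or by MG type. The Month 39 row can mix leavers with completers. Between-visit peaks enter no by-visit table, and no worst-post-baseline summary is named.

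Two clerical points carry none of this weight. SAP 3.3.6 says: "The number and percent of patients with physical examination abnormalities will be summarized by body system and visit", but SAP 4.1 lists no physical examination table. The numbering there skips T04, T05 and T18, so the list may simply be incomplete. Separately, SAP 3.1.2 counts days after baseline while SAP 3.5 uses visit date minus baseline date plus 1 for the same target numbers, a difference of one day.

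**What to change.** (a) Replace the ET paragraph in SAP 3.1.2. Summarise ET results in a separate Early Termination row, with the median and range of actual study day. Place an ET result in a scheduled-visit row instead, never in both, only if it lies within 7 days of that target and that visit was not otherwise done.

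(b) Using scheduled, ET and unscheduled results, add worst-post-baseline rows to the laboratory and ECG shift tables (T14 to T16 and T20). For categorical urine tests, use any post-baseline abnormality. Add minimum and maximum post-baseline value and change to T17 and T19, including QTc. State whether the cardiac-abnormality summary in SAP 3.3.4 counts unscheduled ECGs. Keep unscheduled values out of the by-visit rows.

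(c) At the same time, list the physical examination table and use one day count in SAP 3.1.2 and 3.5.

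**Cost.** SAP wording and programming before the single database lock; no new data. The tables become longer, late-visit rows (notably Month 39) hold fewer patients, and the ET row pools different times, which is why the study-day range is shown. Worst values must be read against length of follow-up and visit frequency. T17 may no longer match a version already run for a DSUR. Scheduled visits would still follow a nearest-to-target rule with no outer limit, so the SAP should say that the 7-day limit applies to ET visits only.
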